## 17.4. VITAL SIGNS

The following vital sign parameters will be collected for this study as per the schedule of events (refer to protocol, Table 3):

- Systolic blood pressure (SBP) (mmHg)
- Diastolic blood pressure (DBP) (mmHg)
- Pulse rate (beats per minute [bpm])
- Oxygen saturation (%)
- Body temperature (°C)
- Weight (kg)

The following summaries will be provided by treatment group based on the SAF analysis population for each vital sign parameter:

- Observed and change from baseline by visit and timepoint
- Number and percentages of subjects with at least one markedly abnormal post-baseline observed value/change from baseline (refer to [Section 17.4.1](#))

All vital sign data will be listed. Vitals signs meeting one of the markedly abnormal criteria in Section 17.4.1 will be identified.

### 17.4.1. VITAL SIGNS MARKEDLY ABNORMAL CRITERIA

Markedly abnormal vital sign observed values and/or change from baseline will be identified in accordance with the following predefined markedly abnormal criteria:

Variable	Unit	Low	High
SBP	mmHg	≤ 90 mmHg AND change from baseline ≤ -20 mmHg	≥ 180 mmHg AND change from baseline ≥ 20 mmHg

Author: [name]

Version Number: 1.0

Version Date: 28Mar2022

Template No.: CS\_TP\_BS016 Revision 6

Reference: CS\_WI\_BS005

Effective Date: 02Dec2019

Variable	Unit	Low	High
DBP	mmHg	≤ 50 mmHg AND change from ≤ -15 mmHg	≥ 105 mmHg AND change from baseline ≥ 15 mmHg
Pulse rate	bpm	≤ 50 bpm AND change from baseline ≤ -15 bpm	≥ 120 bpm AND change from baseline ≥ 15 bpm
Oxygen saturation	%	< 94 %	Not applicable
Body temperature	°C	Not applicable	≥ 38.3 °C AND change from baseline ≥ 1.1 °C
Weight	kg	Percent change from baseline ≤ -7.0 %	Percent change from baseline > 7.0 %

## 17.5. ECG EVALUATIONS

The following electrocardiogram (ECG) parameters will be measured for this study as per the schedule of events (refer to protocol, Table 3):

- PR interval (msec)
- RR interval (msec)
- QRS interval (msec)
- QT (uncorrected) interval (msec)
- Overall ECG evaluation (Investigator's judgment)
  - Normal
  - Abnormal, not clinically significant (NCS)
  - Abnormal, clinically significant (CS)

The following summaries will be provided by treatment group based on the SAF analysis population for each ECG

Author:	[name]	Version Number:	1.0
		Version Date:	28Mar2022
Template No.:	CS_TP_BS016 Revision 6	Reference:	CS_WI_BS005
Effective Date:	02Dec2019		

parameter:

- Observed and change from baseline by visit (for quantitative parameters)
- Number and percentages of subjects with at least one markedly abnormal post-baseline observed value/change from baseline (for quantitative parameters; refer to [Section 17.5.11](#))
- Shift from baseline in overall ECG interpretation to the worst post-baseline assessment

All ECG data will be listed. ECG results meeting one of the markedly abnormal criteria in Section 17.5.1 will be identified.

### **17.5.1. ECG MARKEDLY ABNORMAL CRITERIA**

Markedly abnormal quantitative ECG parameters will be identified in accordance with the following predefined markedly abnormal criteria:

- Observed values for QT (uncorrected) interval will be classified as:
  - > 450 msec
  - > 480 msec
  - > 500 msec
- Change from baseline for QT (uncorrected) interval will be classified as:
  - >30 msec increase from baseline
  - >60 msec increase from baseline

It is to be noted that the previous categories are not mutually exclusive, but cumulative. For example, if a subject worst post-baseline QT post-baseline observed value is 490 mmHg, then this subject will be reported once under QT > 450 msec and once under QT > 480 msec.

## **18. DATA NOT SUMMARIZED OR PRESENTED**

Data that will not be summarized or listed are:

- Results of serology tests performed (i.e., HIV, Hepatitis A, B, and C) at screening for the purpose of

Author:	[name]	Version Number:	1.0
Template No.:	CS_TP_BS016 Revision 6	Version Date:	28Mar2022
Effective Date:	02Dec2019	Reference:	CS_WI_BS005

determining eligibility.

---

Author: [name]

Version Number: 1.0

Template No.: CS\_TP\_BS016 Revision 6

Version Date: 28Mar2022

Effective Date: 02Dec2019

Reference: CS\_WI\_BS005

## APPENDIX 1. PARTIAL DATE CONVENTIONS

### ALGORITHM FOR PRIOR ADVERSE EVENTS, TREATMENT-EMERGENT ADVERSE EVENTS, AND POST-TREATMENT ADVERSE EVENTS

START DATE	END DATE	ACTION
Known	Known/Partial/ Missing	If (AE start date < study drug start date) or AE is a pre-initial dose event, then PRAE.  If study drug start date $\leq$ AE start date and AE start date $\leq$ last drug date_30 and AE is not a pre-initial dose event, then TEAE.  If study drug start date $\leq$ AE start date and AE start date $>$ last drug date + 30 then PTAE
Partial, but known components show that AE started before study drug start date or AE is a pre-initial dose event	Known/Partial/ Missing	PRAE
Partial and known components show that AE started on or after study drug start date	Known/Partial/ Missing	Impute missing AE start day as the first of the month or the first study drug dose date, whichever is later.  If (AE start date < study drug start date) or AE is a pre-initial dose event, then PRAE.  If study drug start date $\leq$ AE start date and AE start date $\leq$ last drug date+30 and AE is not a pre-initial dose event, then TEAE.  If study drug start date $\leq$ AE start date and AE start date $>$ last drug date+30 then PTAE

Note: If an AE started prior to first dose of study drug but worsened after treatment started, it will be reported as a separate adverse event with a new AE start date. A pre-initial dose event is defined as an AE that is entered in the EDC as occurring prior to infusion (Month 0, Day 1).

Author: [name]

Version Number: 1.0

Version Date: 28Mar2022

Template No.: CS\_TP\_BS016 Revision 6

Reference: CS\_WI\_BS005

Effective Date: 02Dec2019

## ALGORITHM FOR PRIOR / CONCOMITANT MEDICATIONS

START DATE	STOP DATE	ACTION
Known	Known or ongoing	If medication stop date < study drug start date, assign as prior; Otherwise, assign as concomitant.
	Partial	If known components of medication stop date show that medication stopped before study drug start date, assign as prior; Otherwise, assign as concomitant.
	Missing, not ongoing	Can never be assigned as prior, therefore assign as concomitant.
Partial	Known or ongoing	If medication stop date < study drug start date, assign as prior; Otherwise, assign as concomitant.
	Partial	If known components of medication stop date show that medication stopped before study drug start date, assign as prior; Otherwise, assign as concomitant.
	Missing, not ongoing	Cannot be assigned as prior, therefore assign as concomitant.
Missing	Known or ongoing	If medication stop date < study drug start date, assign as prior; Otherwise, assign as concomitant.
	Partial	If known components of medication stop date show that medication stopped before study drug start date, assign as prior; Otherwise, assign as concomitant.
	Missing, not ongoing	Assign as concomitant.

---

## APPENDIX 2. LABORATORY ASSESSMENTS

---

### Chemistry (SI unit)

---

- Blood urea nitrogen (BUN) (mmol/L)
- Creatinine (μmol/L)
- Calcium (mmol/L)
- Chloride (mmol/L)
- Potassium (mmol/L)
- Sodium (mmol/L)
- Bicarbonate (mmol/L)
- Glucose (mmol/L)
- Alkaline phosphatase (ALP) (U/L)
- Alanine transaminase (ALT) (U/L)
- Aspartate transaminase (AST) (U/L)
- Albumin (g/L)
- Total protein (g/L)
- Total bilirubin (μmol/L)
- HbA1c, L/L
- Creatinine Clearance, mL/s

---

---

Author: [name]

Version Number: 1.0

Template No.: CS\_TP\_BS016 Revision 6

Version Date: 28Mar2022

Effective Date: 02Dec2019

Reference: CS\_WI\_BS005

### Hematology (SI unit)

---

- Hemoglobin (g/L)
- Hematocrit
- Red blood cells (RBC) (x10E12/L)
- White blood cell (WBC) count total (x10E9/L)
- Platelets (x10E9/L)
- Absolute neutrophils count (x10E9/L)
- Absolute lymphocyte count (x10E9/L)
- Absolute monocyte count (x10E9/L)
- Absolute eosinophils count (x10E9/L)
- Absolute basophils count (x10E9/L)

---

Author: [name]

Version Number: 1.0

Template No.: CS\_TP\_BS016 Revision 6

Version Date: 28Mar2022

Effective Date: 02Dec2019

Reference: CS\_WI\_BS005

### Urine Microalbumin Panel

---

- Urine Microalbumin (mg/dL)
- Urine Creatinine (mg/dL)
- Microalbumin/Creatinine Ratio (ratio)

---

---

Author: [name]

Version Number: 1.0

Template No.: CS\_TP\_BS016 Revision 6

Version Date: 28Mar2022

Effective Date: 02Dec2019

Reference: CS\_WI\_BS005

---

Author: [name]

Version Number: 0.1

Template No.: CS\_TP\_BS016 Revision 6

Version Date: 14Dec2021

Effective Date: 02Dec2019

Reference: CS\_WI\_BS005

## MODIFICATION HISTORY

Unique Identifier for this Version	Date of the Document Version	Author	Significant Changes from Previous Version
0.1	22Dec2021	[name]	Not Applicable – First Version
0.2	20Jan2022	[name]	Planned analyses revised to condense TLF counts
0.3	04Mar2022	[name]	Sponsor review comments addressed
0.4	16Mar2022	[name]	Sponsor review comments addressed
1.0	28Mar2022	[name]	Final version
1.1	26Ago2022	[name]	Text updates to include the changes described in the memo-to-file (22Apr2022) to amend the SAP v1.0, as well as to include the ‘Supplemental Analysis’ described in section 4.3, and additional MMRM in section 16.2.2.1.
1.2	10Nov2022	[name]	Draft version including Day 360 Analysis
2.0	06Dec2022	[name]	Final version sign-off, including Day 360 Analysis

Author: [name]

Version Number: 2.0

Template No.: CS\_TP\_BS016 Revision 6

Version Date: 23Nov2022

Effective Date: 02Dec2019

Reference: CS\_WI\_BS005

---

## 1. INTRODUCTION

This statistical analysis plan (SAP) describes the rules and conventions to be used in the presentation and analysis of efficacy and safety data for protocol AVT001-T1D-01. It describes the data to be summarized and analyzed, including specifics of the statistical analyses to be performed.

This SAP is based on protocol amendment 3, dated 01Feb2021, inclusive of 2 administrative change letters to amendment 3, dated 16Jun2021 and 03Nov2021. The SAP V2.0 amendment was done to include the supplemental analysis at Day 360.

## 2. STUDY OBJECTIVES AND ENDPOINTS

### 2.1. PRIMARY OBJECTIVE AND ENDPOINTS

Objectives	Endpoints
To determine the safety and tolerability profile of three doses of AVT001 (as compared to placebo) in T1D subjects within-vitro -reversible defects in the CD8+ T cell regulatory system.	Incidence of treatment-emergent adverse events (TEAEs).  Clinically significant changes from baseline in clinical laboratory parameters.  Incidence and severity of local IV-site reactions.  Changes from baseline in vital signs and electrocardiograms.  Incidence of severe hypoglycaemic events.

## 2.2. SECONDARY OBJECTIVES AND ENDPOINTS

Objectives	Endpoints

To determine whether, among T1D subjects with in vitro-reversible defects in the CD8+ T cell regulatory system, infusion of AVT001 will lead to an in vivo reconstitution of this system.
 
To determine whether, among T1D subjects with in vitro-reversible defects in the CD8+ T cell regulatory system, infusion of AVT001 will result in amelioration of <math>\beta</math> cell destruction as assessed by stimulated C-peptide.
	
Assessment of the HLA-E-restricted CD8+ T cell regulatory activity (“potency assay”).
 
Changes from baseline in the area under the curve (AUC) of the stimulated C-peptide levels over the first 4 hours of a mixed meal tolerance test (MMTT).
 
Changes from baseline in HbA1c.
 
Change from baseline in insulin usage.
 
Changes from baseline in autoantibody levels.

## 2.3. EXPLORATORY OBJECTIVES AND ENDPOINTS

Although not specifically defined in the protocol, the following endpoints will be examined as exploratory.

Objectives	Endpoints

To explore the effects of infusion of AVT001 on stimulated and unstimulated C-peptide and glucose measurements made over the first 4 hours of a mixed meal tolerance test (MMTT).
	
Changes from baseline in C-peptide and Glucose measured over the first 4 hours of a MMTT:
 
 
• Unstimulated C-peptide
 
• Delta AUC C-peptide
 
• Cmax C-peptide
 
• Delta Cmax C-peptide
 
• Total AUC glucose
 
• Unstimulated glucose
 
• Delta AUC glucose
 
• Cmax glucose
 
• Delta Cmax glucose
 

Author:	[name]	Version Number:	2.0
Template No.:	CS_TP_BS016 Revision 6	Version Date:	23Nov2022
Effective Date:	02Dec2019	Reference:	CS_WI_BS005

[figure not shown]
### 3. STUDY DESIGN

#### 3.1. GENERAL DESCRIPTION

This study is a phase 1 / 2 double-blind, randomized, placebo-controlled study to evaluate the safety and tolerability of AVT001 cell-based therapy, and to assess its potential efficacy for the treatment of type 1 diabetes (T1D). A brief overview of the trial design is outlined in Table A.

**Table A:** Study Design

#### 3.2. SCHEDULE OF EVENTS

Schedule of events can be found in Table 3 of the protocol.

#### 3.3. CHANGES TO ANALYSES FROM PROTOCOL

Potency assay data will be listed in the final Clinical Study Report (CSR).

In addition, as an exploratory endpoint, the potency assay data will be evaluated internally by Avotres and will be reported separately.

A supplemental analysis that will occur after the last subject completes the Month 12 study visit (Day 360) has been added to SAP v2.0.

Author:	[name]	Version Number:	2.0
Template No.:	CS_TP_BS016 Revision 6	Version Date:	23Nov2022
Effective Date:	02Dec2019	Reference:	CS_WI_BS005

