### **16.2.2. ANALYSIS OF SECONDARY EFFICACY ENDPOINTS**

#### **16.2.2.1. Continuous Secondary Efficacy Endpoints**

Observed and change from baseline for C-peptide AUC, HbA1c, total daily insulin dose, total daily basal insulin dose, total daily bolus insulin dose, and each of 4 antibodies will be summarized by treatment group and visit.

For the analysis of C-peptide AUC, a Mixed-effect Model for Repeated Measurements (MMRM) will be performed based on the PD analysis population using the observed-case data. This model will include the change from baseline

Author:	[name]	Version Number:	1.0
		Version Date:	28Mar2022
Template No.:	CS_TP_BS016 Revision 6	Reference:	CS_WI_BS005
Effective Date:	02Dec2019		

variable as the dependent variable, its baseline observed value as covariate, treatment group (active and placebo), visit, HbA1c, BMI, total insulin, potency assay, and treatment group-by-visit interaction as fixed effects. A backward stepwise variable selection process will be used to remove any non-relevant or highly correlated variables before fitting the final model. Restricted Maximum Likelihood (ReML) estimation will be used. An unstructured (UN) covariance structure will be used to model the within-patient error and an adjustment to the degrees of freedom will be made using the Kenward-Roger's approximation. In the event this model does not converge, the heterogeneous Toeplitz, heterogeneous first-order autoregressive (AR(1)), Toeplitz, and AR(1) covariance structures will be tested one after the other in the order listed here i.e., the heterogeneous Toeplitz covariance structure will be tested first and if this model converges, the other covariance structures will not be tested. If this model does not converge, then the heterogeneous AR(1) will then be tested. The same process will be repeated for each covariance structure one after the other as listed above until the model converges.

The Least Square (LS) mean estimates will be provided for each treatment group for each visit along with their standard error (SE). The difference of LS means between the treatment groups (active vs. placebo) and associated SE, two-sided 95% CI, and p-value will also be provided for each visit.

All remaining secondary endpoints (HbA1c, insulin, and auto-antibody levels) will be summarized univariately by generating summaries of the observed values and changes from baseline (both observed and percent changes) by study visit.

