### 16.2. SECONDARY EFFICACY

The secondary efficacy endpoints analyzed in this SAP are:

- Change from baseline in the area under the curve (AUC) of the stimulated C-peptide levels over the first 4 hours of a mixed meal tolerance test (MMTT).
- Change from baseline in HbA1c.
- Change from baseline in total, basal, and bolus daily insulin dose.
- Changes from baseline in autoantibody levels.

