### **16.2.2. ANALYSIS OF SECONDARY EFFICACY ENDPOINTS**

Observed value and change from baseline for C-peptide AUC, HbA1c, total daily insulin dose, total daily basal insulin dose, total daily bolus insulin dose, and each of 4 antibodies will be summarized by treatment group and visit.

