#### **16.2.2.1. Continuous Secondary Efficacy Endpoints – C peptide AUC**

For the primary analysis of C-peptide AUC, a Mixed-effect Model for Repeated Measurements (MMRM) will be performed based on the PD analysis population using the observed-case data. This model will include the change

Author:	[name]	Version Number:	2.0
		Version Date:	23Nov2022
Template No.:	CS_TP_BS016 Revision 6	Reference:	CS_WI_BS005
Effective Date:	02Dec2019		

from baseline variable as the dependent variable, its baseline observed value, age, and time from diagnosis to the first dose as covariates, treatment group (active and placebo), visit, HbA1c, BMI, total daily insulin divided by weight, potency assay, and treatment group-by-visit interaction as fixed effects. The fixed effects and covariates specified in SAP v1.0 were revised per the 22APR2022 memo-to-file to amend the SAP v1.0.

A backward stepwise variable selection process will be used to remove any non-relevant or highly correlated variables before fitting the final model. Restricted Maximum Likelihood (ReML) estimation will be used. An unstructured (UN) covariance structure will be used to model the within-patient error and an adjustment to the degrees of freedom will be made using the Kenward-Roger's approximation. In the event this model does not converge, the heterogeneous Toeplitz, heterogeneous first-order autoregressive (AR(1)), Toeplitz, and AR(1) covariance structures will be tested one after the other in the order listed here i.e., the heterogeneous Toeplitz covariance structure will be tested first and if this model converges, the other covariance structures will not be tested. If this model does not converge, then the heterogeneous AR(1) will then be tested. The same process will be repeated for each covariance structure one after the other as listed above until the model converges.

The Least Square (LS) mean estimates will be provided for each treatment group for each visit along with their standard error (SE). The difference of LS means between the treatment groups (active vs. placebo) and associated SE, two-sided 95% CI for each visit, and *p-value* will also be provided only for Visits at Day 150 and Day 360.

In addition, the following MMRMs for C-peptide AUC will be analyzed as exploratory analyses:

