## 16.3. EXPLORATORY EFFICACY

The exploratory efficacy endpoints analyzed in this SAP are:

- Change from baseline in unstimulated C-peptide of a MMTT.
- Change from baseline in the change in the AUC of C-peptide (Delta AUC) over the first 4 hours of a MMTT.
- Change from baseline in the maximum concentration of C-peptide (Cmax) during a MMTT.
- Change from baseline in the maximum C-peptide levels (Delta Cmax) over the first 4 hours of a mixed meal tolerance test (MMTT).
- Change from baseline in the total area under the curve (AUC) of the stimulated glucose levels over the first 4 hours of a mixed meal tolerance test (MMTT).
- Change from baseline in unstimulated glucose of a MMTT.
- Change from baseline in the change in the AUC of glucose (Delta AUC) over the first 4 hours of a MMTT minus the unstimulated glucose AUC prior to MMTT.
- Change from baseline in the maximum concentration of glucose (Cmax) during a MMTT.
- Change from baseline in the maximum change from baseline concentration (Delta Cmax) of the stimulated glucose levels over the first 4 hours of a mixed meal tolerance test (MMTT)

Author:	[name]	Version Number:	2.0
Template No.:	CS_TP_BS016 Revision 6	Version Date:	23Nov2022
Effective Date:	02Dec2019	Reference:	CS_WI_BS005

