### **16.3.2. ANALYSIS OF EXPLORATORY EFFICACY ENDPOINTS**

#### **16.3.2.1. Continuous Exploratory Efficacy Endpoints**

Observed and change from baseline for all exploratory endpoints will be summarized by treatment group and visit. Univariate summaries of the observed values and changes from baseline (both observed and percent change) will be generated by study visit.

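### The potency assay, endpoint for the first secondary objective, is the only secondary endpoint for which SAP v2.0 plans neither a by-arm summary nor a comparison with placebo

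*Combined protocol and SAP*

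**What the plan says.** SAP v2.0 section 2.2 sets out two secondary objectives and five secondary endpoints. The first endpoint is "Assessment of the HLA-E-restricted CD8+ T cell regulatory activity", the potency assay, which answers the first objective. Section 3.3, on changes from the protocol, then says the potency data will be listed in the CSR and, "as an exploratory endpoint, the potency assay data will be evaluated internally by Avotres and will be reported separately". SAP v1.0 section 3.3 says the same in substance.

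The rest of SAP v2.0 follows section 3.3:

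- Section 16.2 opens with "The secondary efficacy endpoints analyzed in this SAP are" and names C-peptide AUC, HbA1c, insulin dose and autoantibodies.
- Section 16.2.2 gives observed values and changes for C-peptide AUC, HbA1c and three insulin doses, and adds that "each of 4 antibodies will be summarized by treatment group and visit".
- Sections 16.2.2.1 to 16.2.2.4 fit repeated-measures models (MMRM) to the same four endpoints. Potency appears there only on the explanatory side: "potency assay, and treatment group-by-visit interaction as fixed effects".
- Section 16.3 opens with "The exploratory efficacy endpoints analyzed in this SAP are" and gives nine C-peptide and glucose measures from the meal test. Potency is not among them.

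The protocol (Amendment 3) had planned more. The Synopsis (Efficacy Assessment) and section 9.8.1 both leave the potency analysis to be specified in the SAP. Section 9.8 includes the CD8+ system among the outcomes to be presented over time, by MMRM where appropriate. The sample-size text (Synopsis and section 9.2) includes it among the endpoints whose treatment benefit relative to placebo is to be estimated.

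**The concern.** If the SAP is followed as written, the CSR will list individual potency results but give no by-arm result for the first secondary objective. Any statement about reconstitution would rest on a separate sponsor evaluation whose contrast, population and time points the SAP does not fix.

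The missing contrast matters because of how subjects enter the trial. Inclusion criterion 3 requires a CD8+ defect, shown by the screening assay. SAP v2.0 Appendix 1 carries that screening value forward to Day 1, so the selecting measurement is also the baseline. Protocol section 9.8.1 describes a before-versus-after comparison with healthy people as a system control. Selection on a low value followed by remeasurement can produce an apparent gain without any treatment effect. Its size here cannot be worked out from the documents. The randomised placebo arm would control for it, and protocol section 8.8 has placebo subjects assayed too.

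The label is a smaller matter. The protocol assesses all the secondary pharmacodynamic endpoints in an exploratory way (section 5.7), so the word in SAP 3.3 is not new. The gap is the absent analysis.

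**Working it through.** The plan gives no figure on this point to reproduce. The check sets the sections side by side, then asks how precise the missing comparison would be.

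**1. The five secondary endpoints of SAP v2.0 section 2.2**

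| Endpoint | Analysed list (16.2) | By-arm summary (16.2.2) | Between-arm MMRM estimate |
|---|---|---|---|
| Potency assay | no | no | none; explanatory term only |
| C-peptide AUC | yes | yes | 16.2.2.1 |
| HbA1c | yes | yes | 16.2.2.2 |
| Insulin use | yes | yes (total, basal, bolus) | 16.2.2.3 (total divided by weight) |
| Autoantibodies | yes | yes (four) | 16.2.2.4 (each of four) |

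Measures summarised by arm in 16.2.2: 1 + 1 + 3 + 4 = 9. Potency: 0. Section 16.2.1.3 adds three weight-divided insulin measures, which would only widen the contrast.

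**2. Does exploratory status explain it?** The rule for exploratory endpoints in 16.3.2.1 is "Observed and change from baseline for all exploratory endpoints will be summarized by treatment group and visit". It covers nine measures, and potency is not one of them. Potency therefore gets less than endpoints the SAP ranks lower.

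**3. Did it arise from the v2.0 changes?** No. SAP v1.0 modelled only C-peptide AUC but still summarised the same nine secondary measures. Its section 16.2.2.1 says "All remaining secondary endpoints (HbA1c, insulin, and auto-antibody levels) will be summarized univariately", and the parenthesis leaves potency out.

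**4. Does general wording cover it?** SAP v2.0 section 7 promises descriptive statistics by treatment group and visit when applicable, and section 16 says efficacy summaries are by treatment group and visit. Neither names potency. The specific statement in 3.3 promises a listing.

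**5. Are the data available?** Protocol Table 3 schedules blood draws for potency at screening and on Days 90, 150, 270 and 360, so there are four post-treatment results by Day 360.

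**6. Precision, continuous result.** Section 9.8.1 speaks of maximum suppression, but the documents do not state the scale of the transferred result. For a difference in means, in SD units, half-width = t(0.975, df) × √(1/n₁ + 1/n₂).

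- 14:7, df 19: 2.093 × 0.4629 = 0.969
- 16:8, df 22: 2.074 × 0.4330 = 0.898

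Adjusting for the screening value costs one degree of freedom. With zero correlation between screening and follow-up:

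- 14:7, df 18: 2.101 × 0.4629 = 0.973
- 16:8, df 21: 2.080 × 0.4330 = 0.900 (unrounded inputs)

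Allowing for expected chance imbalance in the screening value, with variance factor 1 + 1/(N − 4):

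- N = 21: 0.973 × √(1 + 1/17) = 1.00
- N = 24: 0.900 × √(1 + 1/20) = 0.92

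So adjustment costs little even if it gains nothing.

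**7. Precision, yes/no result.** The counts below are assumed for illustration. Intervals are Newcombe 95% intervals built from Wilson limits.

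- 8/14 versus 0/7: 0.571 (0.140 to 0.786), or 57 points (14 to 79)
- 10/16 versus 2/8: 0.375 (−0.041 to 0.636), or 38 points (−4 to 64)

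**The case against.** The best defence is that this is a disclosed choice of reporting venue. SAP v1.0 section 3.3 announced it before unblinding, the trial has no primary efficacy endpoint, and the sponsor, which runs the assay, will report it separately. Lists headed as covering what this SAP analyses can omit something reported elsewhere. The exploratory list in 2.3 is introduced as holding endpoints that the protocol did not define, whereas potency is defined there. Nothing shows that the separate report will ignore placebo subjects. That report, the table shells and the memo of 22 April 2022 are not in the file, and section 4.4 promises a further SAP amendment.

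Much of this stands. The change was disclosed, the unseen documents limit the point to the SAP itself, and regression to the mean is a possibility of unknown size. The preamble to 2.3 also accounts for potency's absence from that list.

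It does not remove the gap. Disclosure supplies no method. The preamble does not carry over to 16.3, and section 2.2 still calls potency secondary. A promised amendment is an opportunity to add the analysis, but SAP v2.0 does not contain it.

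It is also fair that the half-widths apply to any continuous endpoint at these group sizes and that the yes/no counts are invented. They show what an added estimate could deliver; they do not measure the defect.

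**Conclusion.** The concern holds. Exactly one of five secondary endpoints lacks both a by-arm summary and a between-arm estimate, and it is the one that directly addresses the first secondary objective. The safety objectives are unaffected.

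The conclusion rests on the SAP text alone and on reading section 3.3 as planning no CSR output beyond a listing; that section does not itself say that nothing else will be shown. A between-arm estimate would be descriptive on either scale: a half-width of roughly 0.9 to 1.0 SD if continuous, or an interval spanning more than 60 percentage points under the assumed counts. It would not be a confirmatory test. It would, however, give the CSR a randomised contrast, which a listing does not.

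**What to change.** Reconcile sections 2.2 and 3.3 on whether the endpoint is secondary or exploratory. Then add to section 16.2, for reporting in the CSR:

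1. By-arm, by-visit summaries of maximum suppression and its change from screening.
2. If the result is continuous, the AVT001-minus-placebo difference adjusted for the screening value, with 95% CI, at Day 150 and Day 360.
3. If the result is yes/no, the proportion in each arm and their difference with 95% CI, only where the threshold was documented before unblinding.

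Base any reconstitution conclusion on the between-arm comparison, and label the additions as made after the 17 May 2022 unblinding.

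The cost is a few tables and one model from assays already scheduled. Potency data for the primary analysis were transferred before unblinding (section 4.2), and the amendment due before the Month 24 lock (section 4.4) can carry the change. The drawback is an imprecise estimate specified after unblinding. The by-arm summaries alone would close most of the gap.
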